1.8.2. Known potential benefits

Subject: smART Plus Comparative Study Protocol - Beilinson

As explained above, the various components of the smART+ System must operate as a cohesive system in order to allow feeding optimization as demonstrated in the flowchart below. With validation of the smART+ features during the study, the clinical benefit of the device will be the lowering of risks associated with tube displacement and malpositioning as well as lowering the risks associated with reflux and aspiration.

In addition, the smART+ System is able to continuously measure the patients REE and minimize the risk of overfeeding. Therefore, by reducing overfeeding it not only achieves feeding optimization, but it also reduces the likelihood of reflux episodes due to overfeeding.

2. Objectives and Endpoints

2.1. Primary Endpoint:

 ART MEDICAL PATIENT SAFETY TECHNOLOGY	Number: CRO-C-2822	Date issued: 01-Mar-2021
	Rev.06	Page 15 of 35

Subject: smART Plus Comparative Study Protocol - Beilinson

Optimization of the delivery of nutrition by the smART+ System as compared to standard of care, by automatically calculating and administering enteral feeding better than standard of care (REE or Calorimeter).

Optimization is defined as the ability of the system to provide adequate nutrition (not overfeed or underfeed) when compared to treatment via standard of care.

Evaluation will be conducted based on an analysis and comparison of the following parameters (obtained through the hospital's electronic records for control group and smART+ records for the treated group):

- Patient caloric target set
- Volume of patient nutritional intake value versus actual patient need – this is calculated by assessing the actual nutrition delivered, discarded nutrition in the GRV bags as well as the unused quantity in discarded feed bottles (if applicable).

As part of optimization evaluation, feeding efficiency calculation ((Net nutrition delivered [ml])/ (VTBD [ml])) should be calculated for the days when the patient received enteral feeding that given under medical order, removed from the patient, or stopped feeding that was not renewed until the end of the study. Feeding efficiency should not be calculated for the days that patient has been discontinued from enteral feeding by a medical order.

2.2. Secondary Endpoints:

- Safety

Safe use of the entire system will be assessed based on the occurrence of device related AE or SAE.

- Decrease in ICU length of stay.

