5.2.3. Feeding insertion- group A

Study staff should follow the device instructions for use and specific instructions provided by the console during initial tube placement. Time of tube placement is recorded by the console. Once initial placement is confirmed by the system, verification of correct placement should

 ART MEDICAL PATIENT SAFETY TECHNOLOGY	Number: CRO-C-2822	Date issued: 01-Mar-2021
	Rev.06	Page 19 of 35

Subject: smART Plus Comparative Study Protocol - Beilinson

be performed according to hospital procedures (such as abdominal /chest X-ray /other gold standard).

5.2.4.Vital signs- group A

Vital signs (e.g., temperature, pulse, respirations, blood pressure) should be noted within 10 minutes of feeding tube insertion.

5.2.5.REE measurement- group A

Once the patient has recovered from the process of inserting the feeding tube, a baseline REE measurement should be taken using the smART+ flow sensor and CO₂ sensor.

5.2.6.Feeding program- group A

Once the REE measurement is accomplished, personnel authorized by the hospital should program a suitable feeding program using the smART+ Console and in accordance with hospital procedure.

5.2.7.Ongoing use- group A

If system alerts of tube displacement during ongoing use, the need for tube reinsertion/repositioning should be evaluated and performed as needed.

If system alerts an increase in REE, the message should be evaluated by personnel authorized by the hospital, who should decide if to change the patient's feeding program.

5.2.8.Data recording- group A

The following information will be acquired from the patient's medical chart (recorded in the hospital sources) into the eCRF, for each patient

- Initial screening: as detailed in the study eCRF
- Feeding information: Food types, amounts, rate, water delivery, parenteral nutrition, TPN, other nutritional data
- Gastric residual volume: discard gastric residuals amount, GRV procedure times.
- Medications provided: as detailed in the study eCRF.
- Lab results: patient lab results, as detailed in the study eCRF, and obtained 24 hours prior the feeding tube insertion and during the study, should be recorded in the eCRF.
- Imaging: (X-ray, CT, and alike) performed during the study should be obtained and attached to the eCRF.
- Urine: amounts, rates, times, warnings
- ICU submission and discharge ordering times
- Breathing data reports starting from the ICU admission (FiO₂, PEEP)
- Demographics

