5.3.5. Data recording- group B

The following information will be acquired from the patient's medical chart (recorded in the hospital sources) for each patient:

- Initial screening: as detailed in the study eCRF
- Feeding information: Food types, amounts, rate, water delivery, parenteral nutrition, TPN, Indirect calorimeter and other nutritional data.
- Gastric residual volume: discard gastric residuals amount, GRV procedure times.
- Medications provided: as detailed in the study eCRF.
- Lab results: all patient lab results ordered during the study as well as all available lab results obtained 24 hours prior to study enrollment and added to the eCRF.
- Imaging: patient imaging (X-rays, CT, and alike) performed during the study should be obtained and added to the eCRF.
- Urine monitoring: amounts, rates, times, warnings and all data related to urinary output and diagnosis, and found in the hospital source.
- ICU submission and discharge ordering times
- Breathing data reports starting from the ICU admission (FiO2, PEEP)
- Demographics

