2.3 Length of stay:
Sample size rationale:

The rationale for sample size calculation is based on a difference in length of stay between the tested group (with smART+ System) and the current standard practice (group B).

Sample size justification:

The comparison between groups in ventilation days is reflected by Effect size.

A sample size of 100 in each group will have 90% power to detect an **effect size of 0.46** using a two group t-test with a 0.05 two-sided significance level. [1, 2]

References:

9.2 Endpoints analysis:
9.2.1 General:

All measured variables and derived parameters will be listed individually and, if appropriate, tabulated by descriptive statistics.

 ART MEDICAL PATIENT SAFETY TECHNOLOGY	Number: CRO-C-2822	Date issued: 01-Mar-2021
	Rev.06	Page 31 of 35

Subject: smART Plus Comparative Study Protocol - Beilinson

For categorical variables summary tables will be provided giving sample size, absolute and relative frequency and 95% CI (Confidence Interval) for proportions by study arm.

For continuous variables summary tables will be provided giving sample size, arithmetic mean, standard deviation, coefficient of variation (CV%), median, minimum and maximum and 95% CI (Confidence Interval) for means of variables by study arm.

All tests will be two-tailed, and a p value of 5% or less will be considered statistically significant.

The data will be analyzed using the SAS® version 9.4 (SAS Institute, Cary North Carolina).

9.2.2 Primary endpoint:

The two-sample T-test or Non-parametric Wilcoxon-Mann-Whitney Rank sum test for independent samples (as is appropriate) will be applied for testing the statistical significance of the difference in feeding efficiency between the study groups.

9.2.3 Secondary endpoints:

- The two-sample T-test or Non-parametric Wilcoxon-Mann-Whitney Rank sum test for independent samples (as is appropriate) will be applied for testing the statistical significance of the difference in number of ventilation days (Evaluated by the number of hours of etCO2 from the hospital electronic records) between the study groups.

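### The tested primary variable, ml delivered over an undefined ordered volume, does not show whether energy need was met; an analysis of kcal delivered against kcal need should be added.

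*Combined protocol and SAP*

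**What the plan says.** Section 2.1 (Primary Endpoint) states the aim in these words: "Optimization is defined as the ability of the system to provide adequate nutrition (not overfeed or underfeed". It then lists two parameters to compare between groups. The first is "Patient caloric target set". The second is "Volume of patient nutritional intake value versus actual patient need", worked out from nutrition delivered, nutrition discarded with gastric residual, and feed left in discarded bottles.

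The section gives one formula: "feeding efficiency calculation ((Net nutrition delivered [ml])/ (VTBD [ml])) should be calculated". VTBD is not explained there or in the list of abbreviations.

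Section 9.2.2 has a single primary test, a t-test or rank-sum test used for "testing the statistical significance of the difference in feeding efficiency between the study groups". Section 9.1 sizes the interim analysis on the same variable.

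Elsewhere need is energy. Section 1.3 derives the patient's requirement from REE. Section 5.3.3 refers to a caloric target obtained by REE, calorimeter or another method.

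Section 5.2.8 (device arm) records "Feeding information: Food types, amounts, rate, water delivery, parenteral nutrition, TPN, other nutritional data". Section 5.3.5 (control arm) records "Feeding information: Food types, amounts, rate, water delivery, parenteral nutrition, TPN, Indirect calorimeter and other nutritional data". Neither section, nor section 9.2, plans a conversion to energy.

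**The concern.** The aim is about energy adequacy, while the tested variable is about volume delivered against volume ordered. These are different questions. A group can receive all that was ordered and still be over- or underfed if the order does not match need. Followed exactly, the plan could declare feeding optimized on a significant difference in feeding efficiency without any prespecified comparison of energy received with energy needed.

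A second, smaller issue is that a ml ratio weights every ml equally. If a patient receives formulas of different energy density within the period that one ratio covers, the ratio no longer equals the share of ordered energy delivered.

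**Working it through.** **1. The plan's own figure.** Inputs from section 9.1: 50 per group, effect size 0.70, two-sided alpha 0.025, power 90%.
- Normal approximation: n = 2 × (2.2414 + 1.2816)² / 0.70² = 50.7, so 51 per group. Power at 50 is Φ(0.70 × √25 − 2.2414) = Φ(1.2586) = 89.6%.
- Noncentral t: power 88.8%.

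Both agree with the stated 90% to within rounding. The effect size is standardised, and no mean or SD is given in ml, ratio or kcal units. The power statement therefore neither supports nor excludes an energy-based variable.

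**2. One formula in the ratio.** The documents give no energy densities, so 1.0 to 2.0 kcal/ml is an assumption here. Take 1200 ml delivered of 1500 ml ordered, at density d:

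energy ratio = (1200 × d) / (1500 × d) = 0.80 for every d.

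Density cancels, and the ml ratio is the share of ordered energy delivered. The energy itself is 1200 kcal at 1.0 kcal/ml, 1800 at 1.5 and 2400 at 2.0, all with a ratio of 0.80. Whether any of these meets need cannot be read from the ratio.

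**3. Two formulas in the ratio.** Order 750 ml of each and lose 300 ml from one of them. The ml ratio is 1200/1500 = 0.80 in every row.

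| Densities (assumed, kcal/ml) | Ordered kcal | Energy ratio, 300 ml lost from the thinner formula | Energy ratio, 300 ml lost from the denser formula |
|---|---|---|---|
| 1.0 and 1.5 | 750 + 1125 = 1875 | 1575/1875 = 0.84 | 1425/1875 = 0.76 |
| 1.0 and 2.0 | 750 + 1500 = 2250 | 1950/2250 = 0.87 | 1650/2250 = 0.73 |

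**4. The missing term.** Suppose VTBD is the volume that supplies the caloric target with one formula (an assumption, since VTBD is undefined). Then

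kcal delivered / kcal need = (ml delivered / VTBD) × (caloric target / kcal need).

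The plan tests the first factor only. For an assumed target of 0.7 to 1.3 times true need, a feeding efficiency of 1.00 corresponds to 0.70 to 1.30 of need, and an efficiency of 0.80 to 0.56 to 1.04 of need. The second factor may also differ between arms. The device arm takes its REE from the smART+ sensors (5.2.5), whereas the control arm may use REE, a calorimeter or another method (5.3.3).

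**The case against.** The strongest reply is that the tested ratio is ml over ml and has nothing wrong with its units. That stands. A reader might infer a unit error from the mix of volume and calories in section 2.1. For feeding efficiency this is not so: step 2 shows that density cancels with a single formula. The parameter that sets volume against need has no formula and no test, and the unit of need is not printed beside it. It is an incomplete definition.

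Three other tempting readings also fail.

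- *Patients given the same ml of a dense and a standard formula score the same.* Each patient is scored against his or her own VTBD. If VTBD were the volume supplying an assumed 1500 kcal target, 900 ml would score 900/1500 = 0.60 at 1.0 kcal/ml and 900/1000 = 0.90 at 1.5 kcal/ml.
- *A fixed volume could be anything from slight underfeeding to gross overfeeding.* That is true of energy delivered, but section 9.2.2 does not test volume against a fixed need.
- *Formula choice will bias the comparison between arms.* Hospital-authorised staff set the feeding program in both arms (5.2.6, 5.3.3). Allocation is random, 1:1 and to be balanced within site (5.1), and no section says that the device chooses the formula. Differences after randomisation are possible in an open-label trial, but the documents do not show any.

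It is also fair that the mixed-formula effect is modest and that the documents do not say how often it would arise. Replacing ml delivered / ml ordered by kcal delivered / kcal ordered would change nothing on single-formula days and would still leave need out. None of this supplies the missing comparison with need.

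**Conclusion.** The point holds as a gap between the stated objective and the tested variable. Feeding efficiency is a coherent measure of how much of the order was delivered. It is not evidence that energy need was met, because need is absent from it and the link from VTBD to the caloric target is not stated. This conclusion does not depend on any assumed density.

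The size of the gap does rest on assumptions. An efficiency of 1.00 corresponds to 70% to 130% of need if the target lies between 0.7 and 1.3 times need. The mixed-formula departure is about ±0.04 around 0.80 at 1.0 and 1.5 kcal/ml, and about ±0.07 at 1.0 and 2.0. Reading need as energy is an inference from sections 1.3 and 5.3.3, though a firm one.

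This should be corrected before the analysis. It does not invalidate the ml ratio or the stated power.

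**What to change.** In sections 2.1 and 9.2.2:

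1. Define VTBD and state how it is derived from the caloric target.
2. Convert net delivered volume to kcal/day in both arms, using the energy density of the recorded food type.
3. Add a prespecified between-group analysis of kcal delivered / kcal need. Take need from measured REE or calorimetry where available, and state the rule where it is not. Count deviation in both directions, so that over- and underfeeding cannot offset each other in a group mean.
4. Obtain need on the same footing in both arms. Sections 5.2.5 and 5.3.2 give each arm a baseline measurement, while the schedule in section 5.5 repeats it in the device arm only.
5. Keep the ml ratio as the measure of delivery against the order.

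The cost is small: SAP wording and a density lookup table. Food types and amounts are already collected in both arms. There are two real drawbacks. Discarded gastric residual need not have the formula's energy density, so its energy content must be assumed, and that assumption needs a sensitivity analysis. No power can be given on the kcal scale, because the documents contain no mean or SD for it.

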1.3. Device Description

The smART+ is a comprehensive modular patient care system intended for ICU patients. At the heart of the system is the console which stores, compiles and displays data from the different system modules.

Directly connected to the console is the hub, this is a smaller unit that is positioned adjacent to the patient's bed and serves as a mechanical and communications port for the various modules.

The system's modular arrangement allows the flexibility to add modules over time, at this stage the system comprises the following modules:

- a) The feeding pump is an integral part of the systems console. The feeding pump is controlled by the console and programed by the user using the console's touch screen.
- b) To correspond with the feeding pump, a single use feeding set equipped with an appropriate administration cassette, is loaded into the console.
- c) The feeding tube is equipped with sensors that guide the user toward proper placement of the feeding tube without the need of a conformational x-ray. The sensors also detect reflux events and conveys that information to the console. A balloon on the feeding tube's exterior may be inflated at times of reflux in order to hinder the advancement of gastric content in the esophagus and prevent it from reaching the patient's lungs.
- d) To relieve pressure and remove access gastric content, a disposable Gastric Residual Volume (GRV) set is connected to the proximal end of the feeding tube. The GRV tube passes through a pinch on the system's hub and is only opened when necessary.
- e) The Resting Energy Expenditure (REE) feature is comprised of a disposable flow rate meter and a reusable CO2 detector piece that are added between the patient's endotracheal tube and ventilation tubes. The REE has the capacity to continually measure the patient's energy

[figure not shown]
⁸ Metheny. Effectiveness of an Aspiration Risk-Reduction Protocol. *Norma A. Nurs Res* (2010)

Subject: smART Plus Comparative Study Protocol - Beilinson

expenditure and deduce the patient's nutritional requirements, according to the following equation:

$$REE = \left[3.941 \left(\frac{VCO_2}{RQ} \right) + 1.11(VCO_2) \right] 1.44$$

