1.7. Device Procedure

The use of the smART+ System is substantially similar to the use of commercially available feeding tubes. The smART+ System includes the added feature of facilitating correct tube placement and alerting when tube is displaced during ongoing use. The system will automatically stop feeding if displacement is detected. If a reflux episode is detected by the system, a balloon located on the tube will automatically inflate to prevent gastric content from regurgitating to the esophagus. The balloon inflation parameters are as follows:

- Maximum balloon pressure: 30 mmHg
- Maximum inflation duration: 5 minutes
- Minimum duration between balloon inflations: as long as the previous inflation period

In addition to tube placement, the system allows to obtain REE measurements and calculates the optimized nutritional values required by the patient. Furthermore, the system optimizes feeding by compensating for any lost feeding time or discarded nutritional content that was discarded via the GRV.

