The following information will be recorded by the smART+ console (or accompanying recording equipment) and extracted directly by the sponsor:

 ART MEDICAL PATIENT SAFETY TECHNOLOGY	Number: CRO-C-2822	Date issued: 01-Mar-2021
	Rev.06	Page 20 of 35

Subject: smART Plus Comparative Study Protocol - Beilinson

- Urine monitoring: amounts, rates, times, warnings, trends (and all other data collected by the smART+ System).
- Feeding information: Food types, amounts, rate, fluids delivery (and all other data collected by the smART+ System).
- Gastric residual volume: GRV amounts and times
- Reflux and position data
- REE data
- Breathing data (collected by the smART+ System)
- All other data collected by the smART+ System.

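### The listed data cannot separate feed from other gastric content in discarded residual, so the feeding-efficiency test can favour the arm that ends further from the ordered volume

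*Combined protocol and SAP*

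**What the plan says.** Section 2.1 defines the aim in two directions: "Optimization is defined as the ability of the system to provide adequate nutrition (not overfeed or underfeed"). It assesses intake from what was delivered together with "discarded nutrition in the GRV bags as well as the unused quantity in discarded feed bottles", and scores feeding efficiency as net nutrition delivered (ml) over VTBD (ml). No equation is given for the net quantity. VTBD is not expanded in the text or in the list of abbreviations; I read it as the ordered volume. Section 9.2.2 tests a plain difference in feeding efficiency between groups, by t-test or rank-sum test.

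The residual data are volumes and times:

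- Chart, both arms (5.2.8 and 5.3.5): "Gastric residual volume: discard gastric residuals amount, GRV procedure times".
- Console, group A (5.2.8): "Gastric residual volume: GRV amounts and times".

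Neither list has a field for how much of the residual is feed. Section 1.3 describes the set as there to "remove access gastric content, a disposable Gastric Residual Volume (GRV) set is connected to the proximal end of the feeding tube", so what is drained is stomach content and not feed alone. Section 1.7 says that "the system optimizes feeding by compensating for any lost feeding time or discarded nutritional content that was discarded via the GRV", with no replacement ratio. Section 1.2.1 says that under usual practice such losses often go unreplaced. Section 1.1.3 says that some sites return the residual and others throw it away.

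**The concern.** The text speaks of nutrition in the bags, but the listed data give total volume. Unless a feed share is assumed, the only available calculation subtracts all of it. Any secretion, water or medication in the residual is then scored as lost feed. If the device delivers feed to replace that volume, the subtraction and the replacement cancel in the score, and the surplus in the patient is not seen.

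This bears on the trial's own definition of success. Sections 1.2.1 and 1.8.2 present overfeeding as harmful and its avoidance as a benefit of the device, yet the score can read 100% when retained feed is above the order. If a feed share is chosen after the data are in, it is chosen in an open-label trial (5.1), so it should be fixed beforehand either way.

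**Working it through.** **The plan's own figure.** Section 9.1 states 90% power for an effect size of 0.70 with 50 per group at two-sided 0.025. I obtain 89.6% by the normal approximation and 88.8% by the noncentral t. The figure reproduces and is not in dispute. Section 9.1 gives no mean or SD of feeding efficiency, so the shifts below cannot be put on its scale.

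**Inputs**

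- V = 1,200 ml/day, an assumed VTBD: 50 cc/h × 24, using the rate in 1.1.2.
- G = 200 ml/day discarded in each arm (assumed).
- f = feed share of the residual, unknown, taken from 0 to 1.
- Group A replaces G ml for ml and group B replaces nothing (assumed).
- Otherwise both arms deliver V, and V excludes the replacement volume (assumed).

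**Formulas**

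- Scored: A = (V + G − G)/V = 1; B = (V − G)/V.
- Retained: A = (V + G − fG)/V; B = (V − fG)/V.

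**Results, % of VTBD**

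| f | A scored | B scored | A retained | B retained | Retained gap |
|---|---|---|---|---|---|
| 0 | 100 | 83.3 | 116.7 | 100 | 16.7 |
| 0.25 | 100 | 83.3 | 112.5 | 95.8 | 16.7 |
| 0.5 | 100 | 83.3 | 108.3 | 91.7 | 16.7 |
| 0.75 | 100 | 83.3 | 104.2 | 87.5 | 16.7 |
| 1 | 100 | 83.3 | 100 | 83.3 | 16.7 |

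**Difference between arms.** Scored minus retained is −(1 − f)G/V in both arms, so the gap is 16.7 points on either scale at every f. If discarded volumes differ, the scored gap exceeds the retained gap by (1 − f)(G_B − G_A)/V. Example: f = 0.5, G_A = 100, G_B = 200.

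- Scored: 100 − 83.3 = 16.7 points.
- Retained: A = (1,200 + 100 − 50)/1,200 = 104.2%; B = (1,200 − 100)/1,200 = 91.7%; gap 12.5 points.
- Excess: 0.5 × 100/1,200 = 4.2 points.

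A feed share that differs between arms also biases the gap.

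**Distance from the order.** A is above by (1 − f)G/V and B is below by fG/V. B is closer when f < 1 − f, that is f < 0.5, whatever G and V are. At f = 0.5 both are 8.3 points off. At f = 0.25, A is 12.5 points above and B 4.2 below.

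**How far the 0.5 threshold holds.** If B also loses L ml/day to interruptions that are not made up, while A recovers them, B's distance becomes (fG + L)/V. B is then closer only when f < 0.5 − L/(2G), and never when L ≥ G.

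**The case against.** A reader might infer that part of the measured gain is produced by counting secretions as feed, with the error running in opposite directions in the two arms. The arithmetic does not support this: with equal residuals and equal f both scores shift by the same amount in the same direction. Bias in the difference needs unequal discarded volumes or feed shares. The site differences in 1.1.3 make unequal volumes plausible, but the documents give no values.

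A reader might also infer that the plan says all residual is lost feed. It does not; it speaks of nutrition and nutritional content. Full subtraction is my inference from the data lists. Those lists also include water, medications and other console data, and the eCRF details and user manual are not available here. None of the listed items gives the composition of the residual.

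Three further objections stand as limits:

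- The 100% score depends on ml-for-ml replacement and on a VTBD that does not rise with it. If VTBD includes the replacement, A scores 1,200/1,400 = 85.7%.
- Being above VTBD is not the same as being above measured need.
- Where control residual is returned, its shortfall is not overstated. The chart field already concerns discarded amounts.

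It can also be said that the remaining problem is the choice of metric, because a plain difference does not penalise values above target. That is partly right, but taking absolute deviation of the full-volume score would not cure it: A would still sit at exactly 100%. The unknown feed share has to enter.

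**Conclusion.** The point holds as one about distance from the ordered volume. The planned test of a difference in feeding efficiency is not shown to be biased when the arms discard equal volumes of like composition. The score does not show whether an arm is over or under the order, which is what Section 2.1 says optimization means.

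In the illustration, group A's retained feed lies 0 to 16.7 points above its score, depending on f, and group B's shortfall is overstated by the same amount. Below a feed share of one half the control arm is closer to VTBD although the endpoint favours the device. The sizes are illustrative: the documents give no daily residual, feed share, replacement ratio or VTBD. The one-half threshold also needs equal residuals, full replacement in A only, and no other unreplaced loss in B.

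**What to change.** In Sections 2.1 and 9.2.2:

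1. Define net nutrition delivered and VTBD by one equation used in both arms. VTBD should exclude compensation volume, and only residual actually discarded should be subtracted. State the device's compensation rule as it enters the calculation.
2. Keep the planned test of feeding efficiency.
3. Add a pre-specified supportive analysis of absolute deviation from VTBD, with discarded residual counted as feed at 0% (gross delivered volume), 25%, 50%, 75% and 100%.
4. Report the feed share, if any, at which the conclusion between arms reverses, and word any optimization claim to match.

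These analyses are supportive and not further success criteria, so the sample size basis in 9.1 is untouched. They use volumes already listed for collection. The cost is some analysis work, and possibly a weaker claim if the advantage depends on counting all residual as feed.
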